8.5.14 Assessments in case of suspicion of severe hypersensitivity

If a severe immediate hypersensitivity reaction to the trial product is suspected, blood will be sampled for assessment of anti-drug antibodies including IgE isotype of these after a suitable washout period (minimum 2 weeks). In these cases, it is also recommended to test for tryptase (total and/or mature tryptase) within 3 hours of the reaction if practically feasible. If tryptase is measured, an additional baseline tryptase sample should be taken at the same time as the IgE sample is obtained. Tryptase concentrations (if measured) as well as results of anti-drug antibodies and IgE-isotype antibodies will be collected by Novo Nordisk and included in the final SAE report.

8.5.15 Eye examination

Fundusphotography will be performed in subjects diagnosed with diabetes mellitus before inclusion into the trial (see exclusion criterion 16). It can be performed by the Investigator or a local Ophthalmologist according to local practice at screening and at the end of the main and extension periods. Result of the fundusphotography will be interpreted locally by the Investigator in relation to the trial. To document this, the Investigator must sign and date the result page. The interpretation must follow the categories:

- “Normal”
- “Abnormal, not clinically significant”
- “Abnormal, clinically significant”

In the case of an “abnormal, clinically significant” fundusphotography, the Investigator must comment in the subject notes and, if it occurs at the screening visit, record this on the medical history/concomitant illness form. If the fundusphotography shows proliferative retinopathy or severe non-proliferative diabetic retinopathy the subject must be excluded (see section [6.3](#)).

If a fundusphotography has already been performed no longer than 90 days before randomisation and if the results are available the procedure does not need to be repeated. The Investigator must still interpret, sign and date the fundusphotography. If the fundusphotography was performed before the subject has signed the informed consent Form, it must be documented in the subject notes that the reason for performing the procedure was not related to this trial.

Any clinically significant worsening of the fundusphotography result from baseline must be reported as an AE.

Fundusphotography performed within the 3 weeks before Visits 15 and 29 respectively are acceptable as Visit 15 or Visit 29 data.

8.6 Unscheduled visit

Unscheduled visits can be performed at the investigators discretion if an AE requires additional follow-up or if required by the Novo Nordisk department responsible for safety. Unscheduled visits can take place at any time during the trial from screening until the last visit in the trial. Further, unscheduled visits for re-sampling can take place if laboratory samples are lost or damaged before arriving at the analysing laboratory. This re-sampling will be at the discretion of the Novo Nordisk medically responsible person in collaboration with the investigator.

All assessments performed at any time during the trial can be performed during unscheduled visits with the exception of DXA body composition scan (only permitted if required due to DXA technical reasons), waist circumference and PROs.

Visits/contacts to the site not related to the trial do not need to be reported as an unscheduled visit. Contacts for re-dispensing of trial drug as replacement for lost or damaged trial drug do not need to be recorded as unscheduled visits but need to be recorded in the IV/WRS.

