5.3 Treatment of subjects

Subjects will be randomised in a 2:2:1 ratio to receive either NNC0195-0092 (approximately 112 subjects), Norditropin[®] FlexPro[®] (approximately 112 subjects, open label towards both other arms) or placebo (approximately 56 subjects, double blind towards NNC0195-0092).

Time of injections:

- NNC0195-0092 and placebo subjects will inject themselves once a week s.c. in the morning no later than 10 AM to ensure consistency of PK/PD with previous trials. On site visit days this can be extended until 12:00 PM (noon). Trial drug must not be administered in the morning before relevant visit procedures have been performed (see section [2](#)).
- Norditropin[®] FlexPro[®] subjects will inject themselves daily s.c. in the evening (to reflect standard treatment practice) throughout the trial and only in the morning (no later than 12 PM and at least 12 hours after injection the evening before) during observed trial drug administration. Injections with Norditropin[®] FlexPro[®] the night before blood sampling for anti-hGH antibodies must occur at least 12 hours prior to sampling.

For the first 35-week treatment period, the first dose will be administered by the subject on Day 0 (randomisation), and the last dose will be administered by the subject at home during Week 33. For the extension period, the first dose will be administered in the beginning of Week 35, and the last

dose will be administered by the subject at home during Week 86. No drug will be administered at the Week 34 and Week 87. The maximal treatment duration for a single subject is 86 weeks.

Subjects in all three arms will be trained in the use of the pen-injector and inject themselves under the supervision of the site staff at the visit and will inject themselves at home (see sections [2](#) and [8.7](#)).

Weight loss medications known to affect body weight substantially are not allowed during the trial.

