8.4 Assessments for efficacy

8.4.1 DXA body composition measurement

Body composition will be measured using dual energy x-ray absorptiometry (DXA) whole body scans. The overall process of image acquisition, transfer, central analysis, reporting of results and archiving is described in an **Imaging Charter** prepared by the imaging laboratory. The DXA scan will be performed at Screening (however if it is not possible, it must be performed within 4 calendar days after the screening visit) at the end of the main trial period and at the end of the extension period (see section [2](#)).

The quality of the baseline DXA scan obtained at Visit 1b must be confirmed by the imaging laboratory before the subject can be randomised. The DXA scans will be provided to the imaging laboratory designated by Novo Nordisk for reading in a blinded manner. If a subject withdraws prematurely from the trial, an end-of trial DXA will be performed.

Processes for image acquisition are outlined in an **image acquisition guideline (IAG)**: A single whole body DXA scan will be acquired with the subjects positioned supine, with their arms near their sides on the scanner table. Subjects should be normally hydrated, are not permitted to eat for at least 2 hours prior to the scan, must empty their bladder preceding the scan, and are not allowed to wear any metal or plastic (zippers, snaps, fasteners, grommets, belts, and under-wire bras etc.) or compressive clothing during the scan. Besides the three scans per subject described in this protocol a limited number of repeat scans might be acquired if required due to technical reasons.

Each trial site DXA scanner will need to be qualified by the imaging laboratory prior to scanning subjects. DXA scanner qualification will require submitting baseline DXA instrument local spine phantom quality control (QC) scan results and a whole body DXA scan test transfer. During the trial, all sites must continue to acquire spine phantom QC scans at least three times per week and submit a copy of their QC database (once a month) to the imaging laboratory. Each subject must be

scanned using the same DXA scanner for the duration of the trial. The imaging laboratory must be informed of any scanner software or hardware upgrades. If scanning on the same scanner is not possible or software or hardware upgrades occur, procedures as outlined in the IAG must be followed.

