8.9 Missing data

Investigators will make every effort to ensure all assessments are performed and data are collected. If missing data do occur the reason will be collected via the PD process described in section [19](#) and trends will be monitored on an on-going basis throughout the trial followed by appropriate action (e.g. training of site staff).

If an entire visit is missed and it is not possible to re-schedule the visit within the time window allowed, every effort should be taken to ensure information is collected at a telephone contact. Subjects will be invited for the next scheduled visit according to visit schedule.

If a subject is unable/unwilling to attend the subsequent visit(s) procedures described in section [8.2](#) must be followed.

9 Trial supplies

Trial supplies comprise trial products and auxiliary supplies. Additional details regarding trial supplies can be found in the Trial Materials Manual (TMM).

Trial products must not be dispensed to any person not included in the trial.

NNC0195-0092 PDS290 10mg/1.5ml and NNC0195-0092 PDS290 Placebo must not be used, if the solution does not appear clear to slightly opalescent, colourless to slightly yellow and essentially free from visible particles. Trial product should not be shaken vigorously at any time.

Norditropin[®] FlexPro[®] must not be used, if the solution for injection does not appear clear and colourless. Norditropin[®] FlexPro[®] should not be shaken vigorously at any time.

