2.1.4 Section 2 Flow chart

The nomenclature for the assessments listed in the flowchart will be updated based on the Clinical Data Interchange Standards Consortium (CDISC).

Only one set of footnotes (numbered from 1 to 16) will be displayed after both the main trial and the extension trial flow charts have been displayed.

In addition, the flow chart will be updated according to the relevant changes below.

Flow chart main trial and extension trial:

- Period: ~~Titration period, fixed dose~~
- Trial Periods, visit 1a and visit 1b: *screening*
- Trial Periods, visit 2: *randomisation*
- Trial Periods, visit 3-10 and visit 16-23: *titration*
- Trial Periods, visit 11-14 and visit 24-28: *treatment*
- Visit *number*
- ~~Time (weeks + days)~~ *Timing of visit Weeks*
- Visit window (~~d~~Days)
- ~~Screen~~: replaced with *site*
- ~~Rand~~: replaced with *site*
- ~~EOT 1 and EOT 2~~ replaced with *Site*
- Visit 9 and visit 22, cortisol sample: *x*
- Visit 10 and visit 23, cortisol sample: *x*
- Visit 14 and 28, visit window: ~~+/-2~~
- Visit 14 and 28, visit window: *+2*
- ~~ecap accountability~~
- ACTH ~~stimulation test~~ *ITT*

- Extension trial: ~~Fasting serum~~ cortisol⁷
- ~~Dose adjustment~~ replaced with *New dose of trial product*
- *Reminders: Training in trial product and pen handling*

Footnotes main trial and extension trial:

- 3: ~~All IGF visit may be performed by local sampling service as directed by Novo Nordisk if permitted by the investigator and local requirements.~~ The phone visits can be site visits instead if required by local practice or regulation or at investigator's discretion.
- 3: This footnote will only relate to visit 8 and visit 21.
- 7: This footnote will be added to anti-body sampling for visit 14 and visit 28 and to PK sampling for visit 15.
- 8: The PRO questionnaires must be performed after all fasting related activities and before all other trial-related activity at each applicable visit. TSQM is not assessed at ~~screening~~ *randomisation*.
- 11: ~~If subject is not being treated with glucocorticoid replacement, perform ACTH stimulation test.~~ *If a subject has morning cortisol below normal range, ACTH stimulation test or ITT must be performed. The morning serum cortisol sample collection, which is the basis for the ACTH stimulation test or ITT, should be performed at visit 9, 14 and 22, respectively, before 9 am when the subject is already fasting.*

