11. If a subject has morning cortisol below normal range, ACTH stimulation test or ITT must be performed. The morning serum cortisol sample collection, which is the basis for the ACTH stimulation test or ITT, should be performed at visit 9, 14 and 22, respectively, before 9 am when the subject is already fasting.
12. After trial drug administration.
13. Fundusphotography performed in subjects diagnosed with diabetes mellitus only (see inclusion criterion 10). Fundusphotography performed ≤ 90 days prior to randomisation is acceptable if results are available for evaluation at randomisation.
14. Besides the IGF-I based dose adjustment during the titration period, dose reduction can be considered during the entire study period (including the two titration periods) at the investigator's discretion for safety concerns. If adverse events with a probable relationship to the trial drug are persistent but continuation in the trial is acceptable as judged by the investigator and subject, dose reduction in steps of 25% can be considered. If dose reduction takes place during the titration periods or for deviations to the titration schedule see section 5.3.5.
15. Only for subjects with a history of pituitary adenoma or other benign intracranial tumour. MRI/CT if an MRI or CT scan has not been performed ≤ 9 months (defined as ≤ 270 days) prior to randomisation (results must be available for evaluation at randomisation).
16. The quality of the DXA scan obtained at visit 14 must be confirmed by the imaging laboratory prior to conducting visit 15.
17. **APPLICABLE FOR INDIA ONLY:** *The samples will be analysed at central laboratory.*

Protocol Amendment
Trial ID: NN8640-4054
UTN: U1111-1145-0211
EudraCT No.: 2013-002892-16

~~CONFIDENTIAL~~

Date:
Version:
Status:
Page:

13 January 2015
1.0
Final
1 of 4

Novo Nordisk

Protocol Amendment
no 5
to Protocol, final version 4.0
dated 02 December 2014

Trial ID: NN8640-4054

A multicentre, multinational, randomised, parallel-group, placebo-controlled (double blind) and active-controlled (open) trial to compare the efficacy and safety of once weekly dosing of NNC0195-0092 with once weekly dosing of placebo and daily Norditropin[®] FlexPro[®] in adults with growth hormone deficiency for 35 weeks, followed by a 53-week open-label extension period

Trial phase: 3a

Applicable to Japan

Amendment originator:

[REDACTED]

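### A V14 DXA missed for a non-technical reason has no written recovery route, so a subject still in the trial can have the primary endpoint imputed from placebo

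*Protocol*

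**What the plan says.** **Timing.** The protocol's flow chart (Table 2-1) and section 8.4.1 place DXA at screening, at the end of the main period (V14) and at the end of the extension (V28). V14 is at 33+4d. The amendment to protocol version 2.0 (its section 2.1.4) lists "Visit 14 and 28, visit window" among the flow-chart changes and replaces ±2 days with +2 days. The later flow chart keeps +2. V15 is at Week 35 and has no DXA. Section 5.3 adds: "For the extension period, the first dose will be administered in the beginning of Week 35".

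**Missed visits.** Section 8.9 begins "If an entire visit is missed and it is not possible to re-schedule the visit within the time window allowed" and then asks for information by telephone. It continues: "Subjects will be invited for the next scheduled visit according to visit schedule".

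**Extra scans.** Section 8.6 opens unscheduled visits to the trial's assessments "with the exception of DXA body composition scan (only permitted if required due to DXA technical reasons". Section 8.4.1 likewise says that "a limited number of repeat scans might be acquired if required due to technical reasons". Footnote 16 of the amended flow chart states: "The quality of the DXA scan obtained at visit 14 must be confirmed by the imaging laboratory prior to conducting visit 15".

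**Withdrawn subjects.** Sections 8.2 and 8.4.1 provide an end-of-trial DXA for a subject who withdraws.

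**Analysis.** Section 17.3 imputes missing Week 34 values in every arm from a model fitted to placebo subjects only. The reason given is that withdrawn subjects are taken to have moved to no treatment. Where an intermediate scan exists at time t, the imputed change is scaled by (34 − t)/34 and added to what was observed.

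**The concern.** The endpoint that decides the trial rests on one scan in a three-day slot. A scan missed for a practical reason cannot be collected by telephone, is not scheduled at V15, and falls outside the technical exception in 8.6. Yet 8 to 10 days remain before V15 and the first extension dose, when a scan would be feasible.

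If no scan is taken, the subject has no post-baseline DXA, and the whole change is drawn from the placebo model. For a subject in the NNC0195-0092 arm who took the drug to the end of the main period, that assumption has no stated justification. A subject who withdraws is better provided for, because an end-of-trial scan is requested and its value enters the analysis.

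At stake is avoidable loss of primary-endpoint data, in a protocol whose Amendment 1 records a regulator's request to focus on avoiding missing data.

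**Working it through.** **1. Day count** (Week 0 = day 0)
- V14 opens on day 33 × 7 + 4 = 235 and closes on day 237.
- V15 is day 35 × 7 = 245. The gap is 245 − 237 = 8 to 245 − 235 = 10 days.
- Taking the last weekly dose as day 33 × 7 = 231, V14 falls 4 to 6 days after it and V15 falls 14 days after it.

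**2. The plan's own figures.** Inputs from section 17.1: difference 2.5, SD 4.5, two-sided 5%, 2:1 allocation.
- Exact t-test power with 104 and 52 completers: 0.902 (stated 90%).
- Sample size: 260/0.93 = 279.6, rounded up to 280 (stated 280).
- The SAP's imputation simulation, re-coded with 10,000 trials of 112 and 56 subjects and 100 imputations:

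| Scenario | SAP output | Re-run |
|---|---|---|
| 7.1% drop-out, half with a scan | 89.2%, mean −2.36 | 89.5%, mean −2.37 |
| 15.1% drop-out, none with a scan | 78.7%, mean −2.12 | 78.8%, mean −2.12 |

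The figures reproduce.

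**3. What the simulation leaves out.** Both SAP programs set the endpoint to missing only for drop-outs. Missed scans among subjects still in the trial are therefore planned at zero.

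**4. Effect per missed scan.** An active-arm subject imputed wholly from placebo contributes an expected effect of 0 instead of −2.5. One per cent of the arm therefore moves the expected difference by 0.01 × 2.5 = 0.025 points. The SAP's second scenario agrees: −2.5 × (1 − 0.151) = −2.12.

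**5. Power by assumed miss rate.** The documents give no rate, so a range is shown. It applies to non-drop-outs in both arms, on top of 7.1% drop-out.

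| Miss rate | Power | Mean estimate |
|---|---|---|
| 0% | 89.5% | −2.37 |
| 1% | 88.1% | −2.34 |
| 2% | 87.3% | −2.31 |
| 3% | 86.9% | −2.30 |
| 5% | 84.6% | −2.24 |
| 8% | 81.7% | −2.18 |
| 10% | 79.7% | −2.13 |

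The average loss is (89.5 − 79.7)/10 ≈ 1 power point per 1% missed. Monte Carlo error is √(0.88 × 0.12/10,000) ≈ 0.3 points, so single steps in the table are rough.

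**6. A scan after Week 34 in the present formula.** At t = 35 the factor is (34 − 35)/34 = −0.03. The rule was written for t below 34. Applied as it stands, it would subtract a small part of a placebo change from an observed value.

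**The case against.** The strongest reply is that little may be lost.

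- **A late scan is not excluded.** No passage defines an analysis window or says that an out-of-window scan is discarded. A site that scanned late would record a deviation and still have a value. This stands: a reader might infer that missing the window forfeits the Week 34 value, but the documents do not say so. The difficulty is that 8.6 tells the site not to take the scan.
- **There is some fallback.** Technical repeats are allowed, and the quality check before V15 leaves room for them. A reader might conclude that no fallback of any kind exists. The text supports only the narrower statement that none exists for a non-technical miss.
- **V15 is not blocked.** Footnote 16 might be read as stopping a subject without a V14 scan from proceeding, including one who may not be scanned because of pregnancy. Its wording concerns a scan that was obtained, and 8.9 sends a subject who missed a visit to the next one.
- **A tight window is defensible.** It keeps scans at a similar interval from the last dose. That is a fair reason for the window, but not for preferring no scan to a slightly later one.
- **The bias is conservative, and the complete-case secondary analysis gives a second view.** Both are true, but the placebo-based analysis decides superiority.
- **Detail may sit elsewhere.** Amendment 6 moved DXA detail to the Image Acquisition Guidelines and Site Operations Manual, which are not available here. A rescheduling rule there would still conflict with 8.6.

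**Conclusion.** The point holds in a limited form. Sections 8.6 and 8.9 and the flow chart together leave no written route for a V14 scan missed for a non-technical reason by a subject still in the trial. If no scan is taken, 17.3 imputes the full change from placebo on a rationale that does not describe that subject.

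The size depends on an unknown miss rate. At an assumed 1% to 3% the cost is about 1 to 3 power points and an attenuation of roughly 0.025 to 0.075 percentage points in a planned difference of 2.5. A rate near 10% would be needed to approach the plan's own pessimistic 78% scenario. Against placebo the error makes superiority harder to show, so a positive result is not threatened.

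A reader might use the (34 − t)/34 factor to argue that a scan at V15 would keep almost all of the change. The plan does not support this: the factor scales an imputed placebo change after the last observation and says nothing about how drug effect persists after dosing stops. V28 has the same window, but section 17.5 says extension data are not confirmatory, so changing it is optional.

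**What to change.** 1. **Sections 8.6 and 8.9 and the flow chart:** allow a V14 DXA missed for any reason to be acquired after the window and before the first extension dose, early enough for the imaging laboratory to confirm quality before V15. A scan on the day of V15 leaves no time for that check. The documents give no turnaround time, so the latest acceptable day has to be agreed with the laboratory. Subjects who must not be scanned remain excluded.
2. **Section 17.3:** state that such a scan, and any technical repeat taken after V14, counts as the observed Week 34 value with its date recorded, and that the (34 − t)/34 scaling is not applied to it.
3. **Sensitivity analysis:** repeat the primary analysis with these late scans excluded.

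The cost is a few amendment sentences and no additional planned scan. The downside is that these few scans fall up to about 14 days after the last weekly dose, against 4 to 6 days at V14, so slight attenuation is possible. The sensitivity analysis checks for it.

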8.7 Observed trial drug administration, pen-injector and ecap training

During each of the titration periods all subjects will be trained three times (see section [2](#)) in the use of the pen-injector. After instruction the subject will inject him/herself under observation by trial staff. This can be preceded by injection with a training pen (see section [9.2](#)) which can be administered by the subject into a pad or cushion once (using this test pen is optional).

It is the investigators or delegated staffs responsibility to assess if the subject is capable of following instructions during training and in the directions for use (DFU), so that the subject can deliver the intended dose in a home setting.

During the ecap dispensing and training (see section [2](#)) site staff will instruct the subject in the use of the ecap in accordance with the ecap info card and make sure to replace the injection pen cap with an ecap.

The following will be recorded in the eCRF:

- The subject has received training in use of the pen-injector, including a step-by-step instruction for performing an injection
- The subject has performed an injection on his/her own with corrective feedback provided by site staff
- The subject has received training in the use of the ecap
- Date and time of ecap training
- unique ID of dispensed ecap

